2.4 Subject Withdrawal Criteria

The following are the criteria for considering withdrawal from the study:

- Withdrawal of subject consent/assent. The subject may request for any reason at any time to be withdrawn from the study.
- The Sponsor terminates the study.

If a subject withdraws from the study, the principal reason for withdrawal will be recorded in the electronic case report form (eCRF).

If a study subject fails to attend a study visit at any point during the study period, every effort should be made to keep the subject in the study and conduct all study visits as scheduled; all attempts to contact the subject must be documented. If the subject relocates during the study period, Oculos Clinical Research (Oculos), the clinical research organization, should be contacted to determine if there is a possibility that the subject could continue at another clinical site.

2.5 Study Plan/Procedures

This will be a Phase 3, randomized, multicenter, double-masked, placebo-controlled study to evaluate the extended safety of RVL-1201 Ophthalmic Solution compared to Vehicle (placebo) for the treatment of acquired ptosis. The study will be conducted over 84 days (12 weeks).

Eligible subjects will be randomized in a 2:1 ratio to one of 2 treatment arms and treated for 84 days:

- RVL-1201 Ophthalmic Solution 1 drop in each eye QD in the morning (N = 150)
- Vehicle (placebo) 1 drop in each eye QD in the morning (N = 75)

Both eyes will be treated and assessed.

Following screening evaluations at the Screening/Baseline visit (Day 1), a determination of eligibility will be made, and eligible subjects will be randomized and receive study medication.

Study medication, RVL-1201 or Vehicle (placebo), will be provided in identical-appearing unit-dose vials. The identity of the study medications will be masked to the subject, Investigator, study personnel responsible for ophthalmic evaluations, and Sponsor personnel.

Subjects (or their caregiver, if necessary) will administer study medication QD in the morning during the study period.

Safety follow-up visits will be conducted at Day 14 (Visit 2), Day 42 (Visit 3), and Day 84 (Visit 4).

2.6 Randomization and Masking

Study medication will be randomized in a 2:1 ratio (RVL-1201 Ophthalmic Solution [N = 150]; Vehicle [placebo] [N = 75]). A randomized block design will be used, and the randomization will be created by a biostatistician independent of the trial. Randomization will not be stratified by any factors.

If subjects meet eligibility criteria at Screening/Baseline, Day 1 (Visit 1), sites will access the IWRS to randomize subjects to study treatment and assign the study medication kit to be dispensed. The drug kit and randomization number will be recorded in the subject's eCRF. Study medication from the IWRS-assigned kit will be dispensed to the subject after initial dosing at the study site on Day 1 (Visit 1), on Day 14 ± 3 (Visit 2) and on Day 42 ± 3 (Visit 3).

The study will be double masked. The study medication will be provided in identical-appearing pouches with no labeling indicating the identity of the study group or the contents of the unit-dose vials. The pouches will contain identical-appearing unit-dose vials. Study subjects, Investigators and staff, and study management personnel will be masked to the identity of treatment until after the final database lock.

3. STUDY ASSESSMENTS/ENDPOINTS

3.1 Demographic and Background Characteristics

3.1.1 Demographic/Medical History

A complete medical history will be obtained from each subject. Demographic information including date of birth, gender, race, ethnicity, iris color, and date of informed consent will be recorded.

3.1.2 Concomitant Medications History

All concomitant medications (prescription and OTC) taken at Visit 1 (Screening/Baseline, Day 1) and for 3 months prior to Visit 1 and throughout the course of the study will be recorded in the Concomitant Medications page of the eCRF. Information regarding the dates of first and last dose, site of dosing (e.g., right eye [OD], left eye [OS], both eyes [OU], systemic), and the reason the concomitant medication is being taken must be recorded in the eCRF. When a

concomitant medication has been taken at a stable dose for longer than 6 months, an estimation of the start date is adequate. Standard procedural medications will not be captured in the eCRF but are recorded on a standard procedural medication log provided by Oculos.

3.1.3 Ophthalmic History and Ophthalmic Intervention History

Clinically significant ophthalmic history and ophthalmic intervention history will be documented and will include any previously diagnosed ophthalmic abnormalities and ocular surgeries, including laser procedures.

3.1.4 Urine Pregnancy Test

A urine pregnancy test will be performed at Visit 1 (Screening/Baseline, Day 1) and repeated at Day 84 (Visit 4, End of Treatment) or the Early Discontinuation Visit for women of childbearing potential only.

3.2 External Photography

An external photograph of the subject's face will be taken using the provided digital camera. It is crucial that the same level of ambient lighting be maintained for each photograph throughout the study. The subject will be required to remove mascara and any other eyelid makeup if applicable. The subject will also be asked to relax his/her facial muscles. The photograph will frame the subject's face from mid-forehead to the tip of the nose vertically and from ear-to-ear horizontally. A standardized millimeter ruler label will be placed vertically on the forehead, centered above the eyebrows, as a measurement legend. All measurements (MRD and pupil diameter (PD)) will be made from the digital image or color printed copy of the photograph using a handheld caliper and the millimeter ruler label as the legend.

3.2.1 Marginal Reflex Distance Measurement

The distance from the center pupillary light reflex to the central margin of the upper eyelid is the MRD. The MRD will be measured from the external photograph at Visit 1.

3.3 Safety Assessments

Assessment of the safety and tolerability of RVL-1201 Ophthalmic Solution compared to Vehicle will include bilateral ophthalmic examinations (Snellen VA, PD measurement, SLE/CFS, intraocular pressure (IOP) tonometry, dilated ophthalmoscopy/fundus exam), measurement of vital signs, and recording of adverse events. Subject rating of study medication tolerability will also be obtained. For the timing of all safety assessments, please refer to the Schedule of Procedures.

3.3.1 Vital Signs

Blood pressure (from the same arm, and with the same cuff size, appropriate for arm circumference, throughout study) and heart rate will be measured after at least 3 minutes rest in the sitting position. Vital signs may be repeated once, after at least 5 minutes rest in the seated position, if they are out of range.

3.3.2 Snellen Visual Acuity Assessment

Corrected or uncorrected Snellen VA measurement will be performed with the Snellen eye chart using the subject's current corrective lens prescription, if applicable, at a distance equivalent to 20 feet (6 meters). If the corrected or uncorrected visual acuity is 20/80 or better, no additional refraction is necessary. If corrected or uncorrected visual acuity is worse than 20/80, then an updated refraction must be performed. This refraction must be used for all VA and visual field (if applicable) assessments during the study. The subject must wear the same glasses (if applicable) at each visit. The updated refraction can be placed in a trial frame or phoropter for VA assessments, and the trial frame only for visual field (if applicable) assessments.

For subjects with surgical monovision correction, VA assessment may be conducted in the near vision eye with a near vision reading card held at approximately 14 inches from the subject's eye.

3.3.3 Pupil Diameter Measurement

Pupil diameter will be measured (either horizontally or vertically if top of pupil is not visible in photograph) from the external photograph.

3.3.4 Slit Lamp Exam/Corneal Fluorescein Staining

A routine SLE will be performed to evaluate the anterior segment of the eye, including lids, cornea, conjunctiva, anterior chamber, iris, and lens. Abnormalities will be documented.

Fluorescein staining of the corneal epithelium will be performed in both eyes according to the Investigator's standard of care.

Staining will be graded on a 5-point scale:

0 = No staining

1 = Trace

2 = Mild

3 = Moderate

4 = Severe

3.3.5 Dilated Ophthalmoscopy/Fundus Exam

Direct dilated ophthalmoscopy will include assessment of the optic nerve head for pallor and cupping. A fundus exam consisting of the vitreous, optic nerve, macula, and peripheral retina will be conducted, and the structures will be graded as normal or abnormal. Only tropicamide (Mydriacyl) should be used for this exam. Phenylephrine hydrochloride (Neosynephrine) may NOT be used.

3.3.6 Intraocular Pressure Tonometry

Intraocular pressure will be measured utilizing a Goldmann, Tono-Pen, or iCare tonometer (whichever is chosen, it must be used for the duration of the trial; no combination is permitted) and using the standard of care. If possible, the same calibrated instrument should be used for a given subject throughout the study.

3.3.7 Study Medication Tolerability Assessment

Subjects will be asked to rate the ocular tolerability of the medication according to the following 4-point scale:

- 0 = No discomfort
- 1 = Mild discomfort
- 2 = Moderate discomfort
- 3 = Severe discomfort

3.3.8 Adverse Events

An adverse event (AE) is any untoward medical occurrence in a patient or clinical study subject administered a study medication (pharmaceutical/biological product) that does not necessarily have a causal relationship to this medication. An AE can therefore be any unfavorable and unintended sign (including abnormal laboratory findings), symptom, or disease temporally associated with the use of the study medication, whether or not related to the study medication. Study medication includes the investigational drug under evaluation and the comparator product or vehicle placebo that is given during any phase of the study.

Adverse events will be evaluated and classified for:

- Serious Adverse Events (SAE)
- Relationship to Study Drug
- Severity of Adverse Event
- Outcome

4. SAMPLE SIZE AND POWER CONSIDERATIONS

The sample size for this study is not based on statistical calculations. The sample size was based on the need to obtain sufficient safety data to meet regulatory obligations for the development of RVL-1201.

5. ANALYSIS POPULATIONS

Safety Population:

The safety population includes all subjects who receive at least one dose of double-masked study treatment and have at least one post-dose visit. All analyses will be performed using the safety population according to the treatment received.

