Safety and Tolerability Assessments: Safety assessment will include bilateral SLE/CFS, measurement of pupil diameter from external photographs, dilated ophthalmoscopy/fundus examination, tonometry, Snellen VA using recent correction, if applicable, vital signs (BP/HR), and collection of adverse events (AEs). Tolerability will be rated by the subject on a 4-point scale.

Criteria for Evaluation:

The safety of RVL-1201 compared to Vehicle will be evaluated by the following endpoints:

1. Comparison of ocular and non-ocular AEs by:
 - a. Frequency
 - b. Intensity
 - c. Relationship to treatment
 - d. Serious adverse events
 - e. Adverse events leading to withdrawal of study medication
2. Comparison of subjects with findings on the following measures:
 - a. Slit-lamp examination
 - b. Corneal fluorescein staining
 - c. Pupil diameter
 - d. Dilated ophthalmoscopy/fundus examination
 - e. Tonometry
 - f. Snellen VA (corrected)
 - g. Vital signs (BP/HR)
3. Comparison of tolerability as measured by the tolerability scale

Statistical Methods:

A detailed Statistical Analysis Plan (SAP) will be finalized prior to database lock. Descriptive statistics (n, mean, median, standard deviation [SD], minimum, and maximum for continuous data; frequencies and percentages for categorical data) will be used to summarize study data. No statistical tests will be performed for any of the assessments.

Sample Size:

The sample size for this study is not based on statistical calculations. The sample size was based on the need to obtain sufficient safety data to meet regulatory obligations for the development of RVL-1201.

Analysis Populations:

The Safety population will be used for all analyses. The Safety population includes all subjects who receive at least one dose of double-masked study treatment and have at least one post-dose visit. Subjects will be analyzed according to the treatment received.

Safety Analyses:

Safety endpoints will be reported on the Safety population. Safety assessments include AEs, vital signs (BP/HR), ophthalmic assessments (Snellen VA, bilateral SLE/CFS, measurements of pupil diameter from external photographs, dilated ophthalmoscopy/fundus examination, and tonometry), and a tolerability assessment. Safety assessment will be based on descriptive statistics utilizing actual and change from baseline values, where appropriate, and individual subject listings.

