9.4. Adverse and Serious Adverse Events

9.4.1. Definition of Adverse Events

9.4.1.1. Adverse Event (AE)

An AE is any untoward medical occurrence in a patient or clinical study subject administered a study medication (pharmaceutical/biological product) that does not necessarily have a causal relationship to this medication. An AE can therefore be any unfavorable and unintended sign (including abnormal laboratory findings), symptom, or disease temporally associated with the use of the study medication, whether or not related to the study medication. Study medication includes the investigational drug under evaluation and the comparator product or vehicle placebo that is given during any phase of the study.

Medical conditions/diseases present before starting the investigational treatment are only considered AEs if they worsen after starting the investigational treatment. Abnormal test results constitute AEs only if they induce clinical signs or symptoms, are considered clinically significant, or require therapy.

The occurrence of AEs should be sought by open-ended questioning of the subject at each visit during the study. At each clinic visit, study personnel should ask the following question: "Have you had any problems since your last visit?" AEs also may be detected when they are volunteered by the subject during or between visits or through study assessments.

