9.7. Reporting Adverse Events

All SAEs (related and unrelated) will be recorded following consent and until the final study visit, Day 84 (Visit 4), following the end of treatment exposure. Any SAEs “suspected” to be related to the investigational product and discovered by the Investigator at any time after the study should be reported.

Any SAE that occurs must be reported to Oculos within 24 hours of its occurrence or within 24 hours of learning of its occurrence. Recurrent episodes, complications, or progression of the initial SAE must be reported to Oculos as follow-up to the original episode within 24 hours of the Investigator receiving the information. Information about all SAEs will be collected and recorded on the SAE form. All pertinent medical records and information collected during the treatment and follow-up of the subject should be maintained at the site with a copy emailed to [REDACTED]. The Investigator must assess the SAE relationship and complete the SAE form. Oculos/RevitaLid Inc. may request additional information. Follow-up information (e.g., discharge summary) will be retained in the subject’s chart and a copy will be emailed to [REDACTED]

In addition, all SAEs should be recorded on the Adverse Event eCRF page with the serious question marked “Yes”.

It is the Investigator’s responsibility to notify the approving IRB of any SAEs on a timely basis as instructed by the Sponsor following the Sponsor’s determination of causality.

All subjects who experience an SAE should be followed clinically and undergo the appropriate diagnostic evaluations until stabilization or resolution of the event.

RevitaLid will report all SAEs to the U.S. Food and Drug Administration (FDA) on the appropriate schedule depending if the event is drug related or not drug related, expected or unexpected (based on the available information in the [Investigator’s Brochure](#)).

Any death occurring during the study and follow up period should be reported as an SAE. For any death occurring through the end of the study, regardless of the degree of relationship to study medication, the SAE resulting in the death must be reported to Oculos. A death occurring after completion of the study does not require completion of the SAE form.

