10.1. Day 1 (Visit 1): Screening/Baseline/Randomization/First Dose

Subjects will provide written informed consent before any study-related screening procedures are conducted. For minor subjects, signed informed consent will be obtained from the subject's parent or legal guardian, and assent will be obtained from the subject following IRB guidelines.

Subjects will undergo screening/baseline evaluations to determine eligibility for the study. Following review of inclusion/exclusion criteria, the site will access the IWRS to randomize the subject to study treatment and assign the study medication kit to be dispensed. Subjects (or caregivers, if the subject is not able to self-administer the medication) will receive instruction on administration procedures and administer the first dose. Adverse events will be assessed post dose, and study material accountability will be performed.

Day 1 procedures include the following:

- Informed consent/assent
- Demographics
- Medical and ocular histories
- Urine pregnancy test (females of childbearing potential only)
- Prior and concomitant medications/therapies
- BP/HR
- MRD (from external photograph)
- Pupil diameter measurement (from external photograph)
- Snellen visual acuity
- SLE
- CFS
- IOP
- Dilated ophthalmoscopy/fundus exam
- Review inclusion/exclusion criteria
- Randomization of eligible subjects via IWRS (see Section 8.2)
- Dispense study medication Box 1 per IWRS assignment
- Instruct the subject on use and storage of study medication (see Section 8.6.2)
- The subject (or caregiver, if the subject is not able to self-administer the medication) will administer allocated study medication, 1 full drop in each eye (if a full drop is

not instilled into the eye, the subject will wait approximately 10-15 seconds and administer a second drop). After a full drop is instilled in each eye, the subject should keep the eyes gently closed for approximately 30 seconds.

- AE assessment
- Study medication accountability

10.2. Days 2 through 14

From Days 2 through 14, randomized study medication will be administered in each eye QD in the morning and subjects will return to the clinical site on Day 14 ± 3 days in the morning after instillation of study medication at home. Note: Contact lenses must be removed prior to instillation of study medication and must not be reinserted for at least 15 minutes after study medication instillation. Contact lenses must not be worn during study visits.

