10.4. Early Discontinuation Assessment Procedures

If a study subject is discontinued from study medication before Day 84 (Visit 4) and after Day 1 (Visit 1), procedures performed will include the following:

- Collect all opened and unopened study medication materials (opened and unopened unit-dose vials and pouches) from the subject
- Urine pregnancy test (for females of childbearing potential only)
- Concomitant medication review
- AE assessment
- Study medication tolerability assessment (rating by subject)
- BP/HR (taken after 3 minutes at rest)
- Pupil diameter measurement (from external photograph)
- Snellen VA
- SLE
- CFS
- IOP
- Dilated ophthalmoscopy/fundus exam
- Study medication accountability

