11.3.1. Safety Population

The Safety population includes all subjects who receive at least one dose of double-masked study treatment and have at least one post-dose visit. Subjects will be analyzed according to the treatment received.

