8. SAFETY MEASURES

Safety data will be presented in tables of descriptive statistics and frequency distribution using the safety population. All summary tables will be supported with individual subject data listings.

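### The only analysis set requires a post-dose visit as well as a dose, so a dosed subject who never returns drops out of the AE, SAE and death tables even with an event on record

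*SAP*

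**What the plan says.** SAP section 5 defines one analysis set: "The safety population includes all subjects who receive at least one dose of double-masked study treatment and have at least one post-dose visit". Protocol section 11.3.1 uses the same two conditions ("The Safety population includes all subjects who receive at least one dose of double-masked study treatment and have at least one post-dose visit"), as does the synopsis. The synopsis adds that "The Safety population will be used for all analyses", and Protocol section 11.3 and SAP section 5 agree. Neither document defines a set of all dosed subjects.

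The set carries into the tables through SAP section 8: "Safety data will be presented in tables of descriptive statistics and frequency distribution using the safety population". SAP section 8.9 then specifies the number and percentage of subjects in each group with a treatment-emergent AE, with a treatment-emergent SAE, with a discontinuation due to an AE, and who died.

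Three provisions allow an event to be on record without a later visit:

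- On Day 1, after the first dose at the site, "Adverse events will be assessed post dose, and study material accountability will be performed" (Protocol 10.1).
- "AEs also may be detected when they are volunteered by the subject during or between visits or through study assessments" (Protocol 9.4.1.1).
- "Any SAE that occurs must be reported to Oculos within 24 hours of its occurrence" (Protocol 9.7), or within 24 hours of the site learning of it. A death during the study is reported as an SAE.

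Under SAP 8.9 an event is treatment-emergent if it starts or worsens after randomization. No attendance is required.

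**The concern.** Safety is the trial's sole objective, and descriptive incidence tables are its main output. Whether a dosed subject enters those tables depends on returning to the clinic, which happens after dosing and may be affected by treatment. A subject who tolerates the first drops badly and does not come back, or who dies before a later visit, has a valid treatment-emergent event but is counted nowhere in the incidence tables.

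If non-return is linked to harm, AE, SAE and death incidence is understated. If the link differs between arms, the comparison is distorted as well; the documents give no return rates by arm, so that remains a possibility only. If the subjects lost had no event, rates rise slightly instead.

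The rule also runs against the caution in SAP section 6.3, which counts an AE of missing intensity as severe, one of missing relationship as related, and one of doubtful timing as treatment-emergent. Dropping a whole dosed subject goes the other way.

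**Working it through.** **Who is lost.** The term post-dose visit is not defined. I read it as a visit after Visit 1. Counting the Day 1 post-dose AE check as such a visit would make the second condition almost redundant. On this reading:

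- A subject who attends Day 14, Day 42 or Day 84 (each ±3 days) is kept, including one who misses Day 14 and comes later.
- A subject who attends an Early Discontinuation visit (Protocol 10.4) is kept.
- A subject who attends nothing after Visit 1 is lost, including anyone who dies before a later visit.

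No rule returns the last group to the incidence tables. SAP 6.3 uses observed cases without imputation.

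**Is the clause needed elsewhere?** No. The by-visit and change-from-baseline tables already rest on observed cases, so a subject with no later data contributes nothing to them, with or without the clause.

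**Inputs.** Planned arms are 150 and 75 (Protocol 6.2), which matches 225 × 2/3 and 225 × 1/3. There is no power or sample-size calculation to reproduce (Protocol 11.2, SAP 4). Every event count, event risk and non-return rate below is an assumption.

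**How often a subject might be excluded.** Expected number = 225 × f. Chance of at least one = 1 − (1 − f)^225.

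| Assumed share with no later visit, f | Expected exclusions of 225 | Chance of at least one |
|---|---|---|
| 1% | 2.25 | 0.90 |
| 2% | 4.5 | 0.99 |

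These are exclusions of any kind, most of which may be event-free.

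**Effect of losing k cases.** Incidence = (cases − k)/(N − k).

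| k | RVL-1201, 6 true cases of 150 | Vehicle, 3 true cases of 75 |
|---|---|---|
| 0 | 6/150 = 4.00% | 3/75 = 4.00% |
| 1 | 5/149 = 3.36% | 2/74 = 2.70% |
| 2 | 4/148 = 2.70% | 1/73 = 1.37% |
| 3 | 3/147 = 2.04% | not shown |

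**Effect of losing m event-free subjects, RVL-1201.** 6/(150 − m) gives 6/149 = 4.03%, 6/147 = 4.08% and 6/145 = 4.14% for m = 1, 3 and 5. To offset one lost case, 5/(149 − m) must equal 0.04, so 149 − m = 125 and m = 24. At this rate one lost case outweighs many event-free losses.

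**One early death, RVL-1201, no other death.** The table shows 0/149. With all dosed subjects it shows 1/150 = 0.67%. The exact one-sided 95% upper bound is 1.99% for 0/149 and 3.12% for 1/150.

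**Chance that at least one case reaches the tables.** For a true risk of 2% among 150 dosed, with a share s of affected subjects attending no later visit, this is 1 − (1 − 0.02(1 − s))^150.

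| s | Chance |
|---|---|
| 0% | 95.2% |
| 10% | 93.4% |
| 25% | 89.6% |
| 50% (stress case) | 77.9% |

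**The case against.** The strongest reply is that nothing is hidden. SAP 8.9 lists every event in the database whenever it occurred. SAP 7.2 tabulates the numbers randomized, treated and in the safety population by arm, so a reader can derive how many treated subjects were excluded. Protocol 7.3 and 8.5 ask sites to make every effort to keep subjects attending or, failing that, to complete the early-discontinuation procedures, and such a visit qualifies the subject. The group lost is therefore narrow. Protocol 4.1 describes AEs with once-daily dosing in both earlier studies as mild and not requiring treatment, so heavy informative loss has no support in the documents. No statistical test depends on the set.

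Most of this stands as a limit on size. The exclusion is visible, the group is small, and the upper ends of the illustrations (three of six cases lost, or half of affected subjects not returning) are stress cases. It does not answer the defect. A listing gives no rate and no comparison between arms, retention efforts cannot produce a visit from someone who has died or is lost, and nothing puts the subject back into the incidence tables.

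It can also be said that Visit 1 might count as a post-dose visit. If so, the condition excludes almost no one and serves no purpose. On either reading the text needs repair.

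**Conclusion.** The concern holds. As written, the sole analysis set can remove a dosed subject with a recorded event from both numerator and denominator of the AE, SAE and death incidence tables. This rests on the wording of both documents and on reading a post-dose visit as one after Visit 1. On that reading, a death before any later visit is left out of the death count in the tables.

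The size cannot be determined from the documents and may be zero. Under the assumed counts, one lost case moves a 4.0% rate to 3.4% on RVL-1201 or to 2.7% on Vehicle. At 10% non-return among affected subjects, the chance that a 2% event appears in the RVL-1201 table falls only from 95% to 93%. Confidence is high in the defect of definition, not in any material effect on the results. It should be fixed because safety is the only objective and the repair is cheap. A change made after database lock would look data-driven.

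**What to change.** Delete the condition on a post-dose visit in the Protocol synopsis, Protocol section 11.3.1 and SAP section 5. Define the Safety population as all subjects who receive at least one dose of study medication, analysed by treatment received. State that the AE, SAE, death and AE-discontinuation tables use all dosed subjects, and that by-visit tables use the number observed at each visit, as SAP 6.3 already implies.

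The cost is one clause in three places, with no new data, visits or subjects. The one drawback is that a few subjects with very short follow-up enter the AE denominators, which lowers rates slightly if they had no event. In the illustration above, restoring five such subjects takes 4.14% back to 4.00%.
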